### **REVISION HISTORY**

| Version | Date                | Summary                               |
|---------|---------------------|---------------------------------------|
| 1.0     | 15 November
2019 | Approved version for study initiation |

# Site Principal Investigator Statement

I have read the protocol entitled, "Medela INVIA Motion NPWT system for prophylactic use on surgical incision after cesarean delivery" and I agree to participate and comply with the procedures and requirements as outlined in this protocol. I will provide all study personnel under my supervision with copies of the protocol and access to all information provided by the sponsor.

Signature of Principal Investigator

Date

| 1 Synopsis   |   |  |  |  |
|--|---|--|--|--|
| Study title  | Short Title: The Invia Motion at Cesarean Study   |  |  |  |
| y y | Full Title: Medela INVIA Motion NPWT system for prophylactic use  |  |  |  |
|  | on surgical incision after cesarean delivery  |  |  |  |
| Coordinating   | [name], MPH  |  |  |  |
| investigator(s)  | Division of Maternal Fetal Medicine   |  |  |  |
|  | Department of Ob/Gyn  |  |  |  |
|  | Indiana University School of Medicine   |  |  |  |
|  | [name]  |  |  |  |
|  | [name]  |  |  |  |
| Study objective  | To assess patient centered outcomes of the Medela INVIA Motion
prophylactic NPWT system at cesarean delivery |  |  |  |
| Study design   | A two-center feasibility case series. This study is designed to be  |  |  |  |
| ettaly accign  | performed in accordance with the Declaration of Helsinki, ISO   |  |  |  |
|  | 14155:2011(E), ICH-GCP, Local and National Regulations.   |  |  |  |
| Study duration   | First subject enrolled: December, 2019   |  |  |  |
|  | Expected time of enrolment: 6 Months  |  |  |  |
|  | Last Follow Up Visit: May, 2019 (1 month follow up)   |  |  |  |
| Study sites  | Up to 2 sites   |  |  |  |
| Study population   | Women undergoing cesarean delivery  |  |  |  |
| Inclusion criteria   | 1. Scheduled/non-labor or unscheduled/labor cesarean  |  |  |  |
|  | delivery  |  |  |  |
|  | 2.Gestational age ≥ 23 weeks  |  |  |  |
| Exclusion criteria   | 1.Unwilling or unable to provide consent  |  |  |  |
|  | 2.Non-availability for postoperative follow-up  |  |  |  |
|  | 3.Contraindication to NPWT  |  |  |  |
|  | 
 
Pre-existing infection around incision site
 
   |  |  |  |
|  | Bleeding disorder   |  |  |  |
|  | Therapeutic anticoagulation   |  |  |  |
|  | • Allergy to any component of the dressing (e.g., silver,   |  |  |  |
|  | silicone, adhesive tape)  |  |  |  |
|  | Prior irradiated skin   |  |  |  |
| Primary endpoint   | Patient centered outcomes   |  |  |  |
| y 1   | 
 
Pain scores (scale of 0 - 10) at discharge and
 
  |  |  |  |
|  | postoperative day 30 (+/-2 days)  |  |  |  |
|  | Patient satisfaction scores (scale of 0 - 10) at discharge  |  |  |  |
|  | and postoperative day 30 (+/- 2 days)   |  |  |  |
|  | • Patient satisfaction with aesthetic appearance (scale of 0  |  |  |  |
|  | - 10) at postoperative day 30 (+/- 2 days)  |  |  |  |
| Secondary endpoint   | Efficacy outcome  |  |  |  |
|  | • Composite wound complication including wound infection,   |  |  |  |
|  | would separation, seroma, antibiotics prescribed for  |  |  |  |
|  | presumed SSI within 30 days (+/- 2 days)  |  |  |  |
|  | Safety outcomes:  |  |  |  |
|  | • Skin blistering, allergic reaction, wound bleeding  |  |  |  |
| Study device   | Invia Motion  |  |  |  |
|  |   |  |  |  |
| Reference device   | Not applicable  |  |  |  |
|  |   |  |  |  |

# 4 Abbreviations

| SSI  | Surgical Site Infection         |
|------|---------------------------------|
| NPWT | Negative Pressure Wound Therapy |
| HAI  | Hospital Associated Infection   |

### 5 Introduction

Surgical site infections (SSIs) are now the most common group of healthcare associated infections (HAIs) and are a significant cause of preventable morbidity and mortality in the United States. These infections result in significant patient suffering and excess health care costs up to \$10 billion each year. 1 For these reasons, prevention of HAIs is a top priority for the US Department of Health and Human Services and the Institute of Medicine.2.3 Although several initiatives target HAIs, few are directed at SSIs after cesarean despite the fact that cesarean is the most common major surgical procedure performed in women. In 2013, 1.3 million cesareans were performed in the US and up to 12% of these were complicated by SSIs.

Negative pressure wound therapy (NPWT) is a closed, sealed system that applies negative (or sub-atmospheric) pressure to the wound surface. Used since the 1990s to treat open wounds, experimental evidence suggests that NPWT promotes wound healing by removing exudates, approximating the wound edges, and reducing bacterial contamination.  Three brands of a modified, single-use, battery-powered, portable NPWT devices Prevena™ (KCI USA, San Antonio, TX), PICO™ (Smith & Nephew, Hull, UK) and Invia Motion (Medela) have been FDA-cleared for prophylactic application after wound closure at the time of surgery. Although the precise mechanism of action of prophylactic NPWT is unclear, experimental evidence suggests that NPWT reduces bacterial contamination, edema, and exudates while increasing microvascular blood flow and promoting granulation tissue by inducing mechanical stress that promotes cell growth. Computer and physical models of NPWT applied to closed incisions demonstrate a decrease in lateral tensile stress by 50% and in shear stress by more than 75%, leading to improved apposition of wound edges.

Increasing data suggest potential efficacy of prophylactic NPWT for prevent SSI and other wound complications after cesarean. This is supported by a recent systematic review and meta-analysis which included use of the PICO or Prevena, but was limited by the inclusion of studies with small sample sizes or retrospective design . Two large retrospective studies are underway to define the role of prophylactic NPWT at cesarean. However, none of the studies to date have included use of the Medela Invia Motion device. This study is a prospective case series to assess patient centered outcomes of the Medela INVIA Motion prophylactic NPWT system at cesarean delivery

### 6 Study device(s)

This study will be a prospective study involving the use of 30 FDA-approved Invia Motion devices.

### 6.1 Study device description

The Invia Motion NPWT system is comprised of the Invia Motion pump, Invia Motion Canister/Tubing Set with 150ml capacity, Invia Motion Power Supply and Invia Motion Carrying Case. Additionally, several separately cleared accessories and kits are compatible with the Invia Motion NPWT System.

The Invia Motion pump is a rechargeable battery powered, maintenance-free pump for Negative Pressure Wound Therapy which incorporates a DC-motor with membrane aggregate power actuation in its housing. A user friendly interface, based on 4 tactile buttons and a display, facilitates use and information handling. The Invia Motion NPWT pump provides treatment status through a display and acoustic signals. It is a single patient use pump which provides continuous or intermittent operation and multiple negative pressure selection options. The Invia Motion NPWT pump is portable and its rechargeable battery duration generally exceeds 10 hours, supporting various activities of the patient during the day. Acoustic and optical signals are triggered for variances from the set values as well as for faults.

The Invia Motion NPWT system provides convenience to the patient and provider. Every patient receives their own personal pump for the duration of therapy. The small size and

light weight promote mobility for the patient. The pump is quiet and replacement of the canister is quick and easy.

The Invia Motion NPWT system comes with a discrete carrying case and battery autonomy of up to 10 hours to promote mobility of the patient.

# 6.2 Accessory(ies) description

The Quick-connector interface provides easy and secure attachment between the dressing tubing and the canister tubing.

Invia Foam Dressing Kit with FitPad suction interface consists of:

- Charcoal foam, manufactured using a reticulated polyether and polyurethane hydrophobic material
- FitPad suction interface with Quick-connector
- Transparent film (one or more pieces depending on the kit size)
- All components are packaged together and sterilized using ethylene oxide (EO)
- Invia Foam Dressing Kit is available in four sizes: Small, Medium, Large and X-Large

Invia Gauze Dressing Kit with FitPad suction interface consists of:

- Sterile Kerlix Gauze with PHMB
- Sterile Saline
- Sterile packaged FitPad suction interface with Quick-connector
- Sterile packaged Transparent film (one or more pieces depending on the kit size)
- All components placed together in a plastic bag

Y-connector: Allows treatment of two wound sites on the same patient with a single device.

Transparent film (single sterile item) available as a separate item. Size is 26cm x 32cm.

Invia Silverlon NPWT Antimicrobial Wound Contact Dressing. Provides a barrier to bacterial penetration using silver ions activated by moisture delivered in the dressing which can help reduce infection. Available in two sizes:

- 4" x 5" (10 x 12 cm)
- 5" x 8" (12 x 20 cm)

### \*Not all accessories will be used on all enrolled patients.

### 6.3 Study device intended use

### Invia Motion Devices

The Invia Motion NPWT system is intended to be used by healthcare professionals or adequately trained lay users. Healthcare professionals are responsible to train lay users according to the patient instructions for use and explain all related safety information.

### Intended patient population

The Invia Motion NPWT system is intended to be used on patients only exhibiting conditions as described in the indications for use. The device has not been studied in pediatric patients.

### Intended environment

The Invia Motion NPWT system is intended for use in acute, extended and home care settings.

### Indications for use

The Invia Motion Negative Pressure Wound Therapy (NPWT) system is indicated for patients who would benefit from a suction device (NPWT) as when used on open wounds it creates an environment that promotes wound healing by secondary or tertiary (delayed primary) intention by preparing the wound bed for closure, reducing edema, promoting granulation tissue formation and perfusion, and by removing exudate and infectious material. When used on closed surgical incisions, the Invia Motion NPWT system is also intended to manage the environment of surgical incisions that continue to drain following sutured or stapled closure by maintaining a closed environment and removing exudate via the application of NPWT.

The Invia Motion NPWT system is appropriate for the following indications:

- Acute or subacute wounds
- Chronic wounds
- Dehisced wounds
- Pressure injuries, Pressure ulcers
- Diabetic/Neuropathic ulcers Venous insufficiency ulcers Traumatic wounds
- Partial thickness burns
- Flaps and grafts
- Closed surgical incisions

# **Contraindications**

The Invia Motion NPWT system is contraindicated in the presence of:

- Necrotic tissue with eschar present Untreated osteomyelitis
- Non-enteric and unexplored fistulas Malignancy in the wound
- Exposed vasculature
- Exposed nerves
- Exposed anastomotic site of blood vessels or bypasses Exposed organs

# **Dressing Kits**

The Invia Foam Dressing Kit with FitPad is intended for use in conjunction with the Invia Motion and Invia Liberty NPWT systems. The Invia Motion and Invia Liberty NPWT systems are intended for use in acute, extended and home care settings. Users are directed to the Invia Motion and Invia Liberty NPWT system labeling for additional safety information and instruction for use. To help ensure safe and effective use, the Invia Foam Dressing Kits with FitPad are to be used only with the approved therapy units.

The components of the Invia Foam Dressing Kit with FitPad are packaged sterile and are for single use only. Do not use if sterile package is damaged or opened prior to use. To apply Invia Foam Dressing Kit with FitPad, use clean/aseptic or sterile techniques in accordance with local protocol.

Important: Failure to consult a physician and carefully read and follow all therapy unit and dressing instructions for use and safety information prior to each use may lead to inadequate performance of the product and/or potential for serious or fatal injury. Do not adjust therapy unit settings or use unit without directions from or supervision by the prescribing physician.

The Invia Foam Dressing Kit with FitPad in conjunction with Invia Motion and Invia Liberty NPWT systems is indicated for patients who would benefit from a suction device (NPWT) as when used on open wounds, it creates an environment that promotes wound healing by secondary or tertiary (delayed primary) intention by preparing the wound bed for closure, reducing edema, promoting granulation tissue formation and perfusion, and by removing exudate and infectious material. When used on closed surgical incisions, the Invia Foam Dressing Kit with FitPad is also intended to manage the environment of surgical incisions that continue to drain following sutured or stapled closure by maintaining a closed environment and removing exudate via the application of Negative Pressure Wound Therapy. The Invia Foam Dressing Kit with FitPad is appropriate for use for the following indications:

- Acute or sub-acute wounds
- Chronic wounds
- Dehisced wounds
- Pressure injuries, Pressure ulcers
- Diabetic/neuropathic ulcers
- Venous insufficiency ulcers
- Traumatic wounds
- Partial thickness burns
- Flaps and grafts
- Closed surgical incisions

# 6.4 Procedure

Primary or repeat cesarean delivery

# 6.5 Training

The Invia Motion Endure NPWT system is an equivalent system to NPWT devices widely used at this Facility.

Onsite, face-to-face training will be provided by Medela representatives to research staff who will be involved in the study.

Research and/or clinical staff will instruct the patient on what to do during the treatment. Patient will be provided with Invia Motion Endure NPWT system Patient IFU and NPWT APP.

Research and clinical staff trained by Medela representatives will be allowed to train any additional staff for the study.

# 6.6 Study device management

# 6.6.1 Device complaints/malfunction of device

Complaints are any deficiencies with regards to the study device, instructions for use, operator's manual and other product related documentation. Device complaints may or may not involve a clinical event/in this case an adverse device effect to the patient in which case the definitions in the section of adverse event reporting of this clinical investigation plan shall also apply.

# 6.6.2 Reporting of complaints

[figure not shown]
Any complaints on the device, instructions for use, operator's manual and other product related documentation shall be reported to the CRA using the appropriate reporting forms. Whenever possible in case of malfunction of the study device or part of study device, the product in question shall be returned to the Sponsor for investigation. The appropriate procedure for such return shall be provided by the Sponsor prior to starting the clinical investigation.

# 6.6.3 Inventory and accountability records

Adequate records of study product and disposition will be maintained by the research staff at both study sites. The purpose of these records is to ensure regulatory authorities that the study product will not be distributed to any person who is not a study subject under the terms and conditions set forth in the protocol. The study product is to be prescribed by the Investigator or designees and may not be used for any purpose other than that described in this protocol. At study completion, all study products must be returned to Medela USA.

# 6.6.4 Device storage

Devices will be stored in a secure storage location at the site.

# 6.6.5 Device return

Upon completion of the study, all unused devices must be returned to Medela USA according to the local agents' instruction.

# 7 Risk analysis

# 7.1 Risks

The Single Use Prophylactic Negative Pressure Wound Therapy System received FDA marketing approval in 2012. As of September 2015, we identified two reports on the FDA website of blistering at the site of application from the PICO device. A third report of a minor burn from the PICO pump device occurred in a patient after neurosurgery while still unconscious. The patient was found to have been lying on the pump device for a prolonged period of time. Case series suggest approximately 10-15% rate of skin irritation and blisters at the device application site. The majority (~90%) did not require treatment beyond removal of the device. Moreover, adverse events noted with NPWT after cesarean were minor and comparable in frequency to standard dressing.

# 7.2 Benefits

The study is not designed to provide direct benefits to research participants. Nonetheless, if our hypothesis that women will have lower rates of SSIs after cesarean with use of prophylactic NPWT than with standard care is correct, then patients will have the benefits lower rates of SSIs. More importantly, results from this study have the potential to improve outcomes for women undergoing cesarean delivery.

# 7.2.1 Risk-to-benefit rationale

Because the anticipated risk to participants is minimal, the risk-benefit ratio is very favorable.

# 8 Investigational plan

# 8.1 Study objectives

To assess patient centered outcomes of the Medela INVIA Motion prophylactic NPWT system at cesarean delivery.

# 8.2 Study hypotheses

We test the hypothesis that the Medela INVIA Motion prophylactic NPWT system will be feasibly used at cesarean delivery with significant patient satisfaction.

# 8.3 Claims to verify

Feasibility of the Medela INVIA Motion prophylactic NPWT system at cesarean delivery with significant patient satisfaction.

# 8.4 Risks to assess

<10% device related adverse events including skin blistering, allergic reaction and wound bleeding.

# 8.5 Study design

This study will be a two center case series of women undergoing caesarean delivery conducted at two medical centers in Indianapolis, Indiana.

All patients meeting inclusion criteria will be included. All enrolled patients will receive the Medela INVIA Mation prophylactive NPWT device.

# 8.6 Primary Endpoint

Patient centered outcomes

- Patient satisfaction scores (scale of 0 10) at discharge and postoperative day 30 (+/- 2 days)
- Pain scores (scale of 0 10) at discharge, at removal and postoperative day 30 (+/-2 days)
- Patient satisfaction with aesthetic appearance (scale of 0 10) at postoperative day 30 (+/- 2 days)

# 8.6.1 Secondary endpoints

Efficacy outcome

• Composite wound complication including wound infection, would separation, seroma, antibiotics prescribed for presumed SSI within 30 days (+/- 2 days)

Safety outcomes:

• Skin blistering, allergic reaction, wound bleeding

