# 10.4 Visit B: Post Procedure until Discharge

- Patients will be monitored daily while in the hospital by clinical staff and/or research staff for complications.
- The negative pressure wound therapy dressing will be removed on the day of discharge. If the patient remains hospitalized for more than 7 days, the dressing will be removed on postoperative day 7.
- Replacement of any dressing that is saturated.
- If a patient develops infection with the NPWT device in place the device will be removed and the patient given standard SSI therapy as outlined below.
- Patients will be educated about the signs and symptoms of infection and other study outcomes and encouraged to call their provider if these should arise.
- Research staff document inpatient course regarding SSI.
- Management of surgical site infections will follow the Practice Guidelines of the Infectious Diseases Society of America.

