# 12.1 Adverse Event Reporting

During the course of this clinical investigation adverse events might occur. For the purposes of this study the following categories of adverse events are relevant for reporting:

- Adverse Event of Special Interest (AESI)
- Serious Adverse Event (SAE)
- Adverse Device Effect (ADE)
- Serious Adverse Device Effect (SADE)

Subjects will be evaluated for adverse events in the following manner:

- Routine monitoring by physicians, nurses and research team during inpatient stay, with data obtained from the subject's EMR by research staff.
- Patients will be scheduled for standard of care follow-up with their provider at 1-2 weeks and 4-6 weeks postpartum. Research staff will review the subject's EMR after 6 weeks postpartum.
- Medical records will be sought for any patient or provider-reported complications.

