# 12.2 Adverse Events of Special Interest (AESI)

For this study, abnormal laboratory findings (e.g., clinical chemistry, hematology) or other abnormal assessments (e.g., electrocardiogram, X-rays, vital signs) per se are not reported

as AEs. Only Adverse Events of Special Interest (AESI) defined below will be recorded on the CRFs and in the subject's chart.

For this study, AESIs refer to:

- Mild/moderate reactions:
  - o Skin blisters
  - o Wound bleeding
  - Allergic skin reaction

Any current condition that is recorded as a pre-existing condition in the medical history, unless there is a change in nature, severity, or degree of incidence, is not an AE.

Relation to the clinical investigation device will be assessed by help of the following criteria:

- Related
- Not related

Relation to the procedure will be assessed by help of the following criteria:

- Related
- Not related

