### 12.4 Adverse Device Effects (ADE) & Serious Adverse Device Effects (SADE)

An adverse device effect is an adverse event related to the use of a study medical device

This definition includes adverse events resulting from insufficient or inadequate instructions for use, deployment, implantation, installation, or operation, or any malfunction of the investigational medical device.

This definition also includes any event resulting from user error or from intentional misuse of the investigational medical device.

An ADE is classified as serious if it has resulted in any of the consequence characteristics of a serious adverse event or that might have led to any of these consequences if suitable action had not been taken or intervention had not been made or if circumstances had been less opportune.

If an ADE or SADE has occurred any retrievable part of the Invia® Motion™ Endure NPWT system should be returned to Medela AG for analysis. If there is also a suspected relation to accessory material (guide wire etc.) the accessory material in question should also be sent to Medela AG for analysis.

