# Relationship of Reportable Events:

An Investigator must make the determination of relationship to the drug for each AESI/ADE. The relationship to the device should be assessed using the guidelines presented in the table below.

| Relationship to
Device | Description  |
|---------------------------|--|
| Related                   | 
 
Previously known harmfulness of device; or
 
Follows a reasonable temporal sequence from administration of the device; or
 
 |

|           |   |
|------------------|---|
|                  | 
 
Follows a known or expected response pattern to the suspected
 
   |
|                  | intervention; or  |
|                  | 
 
Is confirmed by stopping or discontinuing the device; and
 
   |
|                  | 
 
That is not explained by any other reasonable hypothesis
 
  |
| Probably related | 
 
Follows a reasonable temporal sequence from the time of study
 
   |
|                  | intervention; and/or   |
|                  | 
 
Follows a known response pattern to the study device; and
 
   |
|                  | 
 
Was unlikely to have been produced by other factors such as the
 
   |
|                  | subject's clinical state, therapeutic intervention, or concomitant therapy  |
| Possibly related | 
 
Follows a reasonable temporal sequence from the time of study
 
   |
|                  | intervention; and/or   |
|                  | 
 
Follows a known response pattern to the study device; but
 
   |
|                  | 
 
Could have been produced by other factors such as the subject's
 
   |
|                  | clinical state, therapeutic intervention, or concomitant therapy  |
| Unlikely related | • Does not follow a reasonable temporal sequence from the time of study   |
|                  | intervention; and
• Was likely produced by other factors such as the subject's clinical state  |
|                  | 
 
Was likely produced by other factors such as the subject's clinical state,
therapeutic intervention, or concomitant therapy but for which
 
 |
|                  | relationship cannot be definitely ruled out   |
|                  |   |
| Not related      | The adverse event can be determined with certainty to have no   |
|                  | relationship to the study device  |

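### No step requires a non-serious wound infection, separation or seroma to be rated for relation to the device, even when it leads to device removal

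*Combined protocol and SAP*

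**What the plan says.** All references are to the combined protocol and SAP.

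- **Endpoints (8.6.1).** The efficacy outcome is "Composite wound complication including wound infection, would separation, seroma, antibiotics prescribed for presumed SSI within 30 days". The safety outcomes are "Skin blistering, allergic reaction, wound bleeding".
- **Risk to assess (8.4).** "<10% device related adverse events including skin blistering, allergic reaction and wound bleeding".
- **Device removal.** Section 10.4 states "If a patient develops infection with the NPWT device in place the device will be removed". Section 10.6 leaves discontinuation after any wound complication to the investigator or the patient's provider. Section 9.3 makes device removal a reason for withdrawal, with the reason to be investigated and documented.
- **Reporting categories (12.1).** The text reads "For the purposes of this study the following categories of adverse events are relevant for reporting" and lists four: AESI, serious adverse event (SAE), ADE and serious ADE.
- **Recording rule (12.2).** "Only Adverse Events of Special Interest (AESI) defined below will be recorded on the CRFs". The AESIs are skin blisters, wound bleeding and allergic skin reaction, under a heading that confines them to mild or moderate reactions. Relation to device and to procedure is rated on two levels.
- **ADE definition (12.4).** "An adverse device effect is an adverse event related to the use of a study medical device".
- **Relation rating (12.5, Relationship of Reportable Events).** "An Investigator must make the determination of relationship to the drug for each AESI/ADE". The word drug is evidently a slip, since the next sentence refers to the device. The table there has five levels.
- **Onward reporting (12.5) and source records (13).** Non-severe AESIs and ADEs go to the sponsor every 6 months and to the IRB at renewal; SAEs go to both within 24 hours. The source record must hold every AESI, SAE, ADE and serious ADE.

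**The concern.** The protocol treats wound complications as relevant to the device: infection around the incision is an exclusion listed as a contraindication (9.2), infection during wear leads to removal (10.4), and any wound complication raises the question of discontinuation (10.6). Yet the same events sit only under efficacy, while a minor blister gets an adverse event report and a relation rating.

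This matters more than it would in a controlled trial. With a comparator, an excess of wound complications could be seen by comparing arms. Here every woman receives the device (8.5, 10.1), so the composite rate alone cannot show whether the device contributed. The case-level relation rating is the only planned means of attributing a wound harm to the device. If that rating is not required, an infection under the dressing or a separation can appear in the efficacy table and be missing from the device-related events that 8.4 sets out to assess.

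**Working it through.** The plan gives no figure to reproduce on this point; 15.1 states a sample of 30 without a formal calculation. The check is mainly a reading of the sections against each other, with a little arithmetic for scale.

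**Step 1. Follow a non-serious wound infection, separation or seroma through the four categories of 12.1.**

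| Category | Does the event enter it? |
|---|---|
| AESI (12.2) | No. The list has three other items. |
| SAE (12.3) | No, by assumption. It would if it led to or prolonged hospitalization, or met another criterion there. |
| ADE (12.4) | Only if related to the device. |
| Serious ADE (12.4) | Only if related, and if it met the seriousness test or might have done so without intervention. |

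**Step 2. Look for what triggers the relation judgement.** The rating in 12.5 is required for each AESI or ADE. For these events the AESI route is closed, so the rating is required only if the event is already an ADE. It is an ADE only if it is related. The requirement therefore presupposes the answer it is meant to obtain.

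**Step 3. Look for another trigger.** The two-level rating in 12.2 belongs to the AESI section. The report contents in 12.5 include relationship to treatment, but for events that qualify for a report. The schedule in 10.5.2 offers the AE/SAE form at three contacts, only where applicable. Sections 9.3, 10.4 and 10.6 deal with removal, discontinuation and withdrawal without asking for a relation rating. No trigger was found.

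**Step 4. Check the recording rule.** Read literally, 12.2 keeps everything except AESIs off the CRFs as adverse events. That conflicts with 12.1, 12.4, 12.5 and 13, which make SAEs, ADEs and serious ADEs reportable or recordable.

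**Step 5. Scale.** Inputs: n = 30 (sections 6 and 15.1); the 10% figure (8.4); a background surgical site infection (SSI) rate of up to 12% (section 5). The rates of 3% and 6% are my assumptions, to show a range.

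- One event is 1/30 = 3.3 percentage points.
- 2/30 = 6.7%, exact (Clopper-Pearson) 95% CI 0.8% to 22.1%.
- 3/30 = 10.0%, exact 95% CI 2.1% to 26.5%.
- Expected SSIs = n × p, and P(at least one) = 1 − (1 − p)^30:

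| Assumed SSI rate p | Expected in 30 | P(at least one) |
|---|---|---|
| 3% | 0.9 | 0.60 |
| 6% | 1.8 | 0.84 |
| 12% | 3.6 | 0.98 |

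The expected counts cover all SSIs, serious or not, before or after device removal, and whatever their cause. They show that at least one SSI is more likely than not over this range. They do not estimate unrated or device-related events.

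**The case against.** The strongest reply is that the plan already has a route. The ADE definition has no seriousness threshold and no closed list, so a non-serious infection or separation judged device-related is an ADE, is reported to the sponsor and IRB under 12.5, and belongs in the source record under 13. Staff assess adverse events at the discharge contact, SSIs are actively sought (10.5), and records are sought for any reported complication (12.1). Withdrawal after device removal is investigated and documented (9.3). The dressing comes off at discharge, or on day 7 of a longer stay (10.4), so a complication that ends wear arises in an inpatient; if it prolongs the stay it is an SAE, reported within 24 hours. Finally, 8.4 introduces its three events with the word including, so a device-related wound complication is not excluded from that count.

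Most of this stands, and it rules out stronger readings. A reader might infer that these events fall outside every reporting category unless serious, or that they are never rated or reported. The ADE and SAE routes show otherwise. A reader might also take 3.6 of 30 as the number of unrated events. It is a ceiling on SSIs under the upper background rate; the documents give no split by seriousness, timing or relation. Nor does one event overturn a verdict: 8.4 names a risk to assess, section 15 attaches no test or decision rule to the 10%, and the intervals for both 2/30 and 3/30 include 10%.

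The reply does not supply a trigger. The ADE route works only if an investigator raises the question of relation unprompted, 9.3 asks for a reason rather than a causality rating, and 12.2 points staff the other way. The open wording of 8.4 makes the gap matter, because events that belong in its count need not be assessed for it.

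**Conclusion.** The point holds as a gap in required assessment, not as a loss of data. Non-serious wound infection, separation and seroma are captured as outcomes, but no step requires a device-relation rating, including when the event leads to device removal. Rating and adverse event reporting therefore depend on an unprompted judgement, and the recording rule in 12.2 contradicts other parts of the plan.

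The device-related rate under 8.4 may be understated by 3.3 percentage points for each device-related wound complication not identified as such. How many there would be cannot be derived from the documents. The conclusion rests on reading 12.2 and 12.5 as written and on reading the list in 8.4 as open. In a 30-woman feasibility series this will not settle the safety question either way, but the correction is cheap and attribution has no other planned source.

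**What to change.** 1. Require an adverse event form, with onset, severity and relation to device and to procedure, for every wound infection, wound separation and seroma. An infection presumed from an antibiotic prescription is included and counted once; the prescription is not a separate event. Either add these to the 12.2 list outside its mild/moderate heading, or put a separate sentence in 12.5.
2. Count those judged device-related under 8.4. Leave the composite in 8.6.1 unchanged.
3. Reconcile the recording sentence in 12.2 with 12.1, 12.4, 12.5 and 13, so that SAEs, ADEs and serious ADEs are clearly recorded too.
4. Use one relation scale in 12.2 and 12.5. If it has more than two levels, state which count as device-related for 8.4.

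The cost is a short amendment and a few extra forms, largely using data already collected for the composite. The device-related rate may come out slightly less favourable. No treatment rule or endpoint changes.
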